We will employ a single-center, parallel, randomized, prospective design. Enrolled patients will be assigned to one of two treatment arms using a block randomization scheme: transforaminal cervical epidural corticosteroid injection or lateralized interlaminar cervical epidural corticosteroid injection. Baseline data will be collected including duration, location, and character of pain; numerical pain scale (NRS); neck disability index (NDI); EQ-5D; and work ability index (WAI) (see Outcome Measures below). All procedures will be performed under CT fluoroscopy on the same scanner. The cervical level of injection for patients in both treatment arms will be at the discretion of the treating physician and will be based on symptoms (e.g., dermatomal distribution of pain) and imaging findings. All injections will be performed by a board certified radiologist with a certificate of added qualification in neuroradiology and at least five years of experience in CT fluoroscopy-guided spine injections. Patients and outcome assessors (clinical research coordinator) will remain blinded to the treatment assignment throughout

the study. In order to maintain blinding of patients and appropriate study personnel throughout the trial, billing / charges will be held until the patient reaches the final endpoint of the study or withdraws from the study. The research coordinator will be the study personnel who records the billing at this point, however, all outcome assessments will have been completed already ensuring that they remain unbiased. The treating physicians are unable to be blinded, as they will be aware of the type of patching material used. The effectiveness of patient blinding will be assessed using the Bang Blinding Index prior to discharge on the day of the procedure (8). Patients will become unblinded to their treatment assignment at the end of their participation in the study (either at the conclusion of the study after the final outcome measure time point (i.e. 4 months) or if they elect to withdraw from the study at any time).

Transforaminal Cervical Epidural Corticosteroid Injections (TFESI)

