Adult patients with unilateral cervicogenic upper extremity radiculopathy (with or without accompanying neck pain) and a baseline numerical pain scale (NRS) score > 4 will be recruited from the Duke Radiology and Orthopaedic spine intervention clinics. Exclusion criteria include: (a) recent (i.e., < 2 months) cervical spine surgery, (b) recent (i.e., < 1 month) cervical epidural or upper extremity corticosteroid injection, (c) contraindication or inability to undergo procedure, (d) inability to provide informed consent, (e) expected inability to complete follow-up assessment, or (f) a contraindication to receiving contrast material (precluding an epidurogram). We aim to recruit 116 patients over 1 year. This number is based on the historical number of patients treated with unilateral

cervical radiculopathy, our sample size determination (see Statistics), and previously published studies in the lumbar spine (7).

We estimate that approximately 1000 patients will be screened over one year in order to reach our target recruitment of 116 patients.

Subject Recruitment and Compensation

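### Recording each patient's billing as they finish means assessor blinding is not assured for other patients' later 4-month assessments

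*Combined protocol and SAP*

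**What the plan says.** In Design & Procedures, under Cervical Epidural Corticosteroid Injections, the plan identifies the assessor and makes an unqualified claim: "Patients and outcome assessors (clinical research coordinator) will remain blinded to the treatment assignment throughout" the study. The same section sets out how billing is handled. Its purpose is stated as "In order to maintain blinding of patients and appropriate study personnel throughout the trial", so the protocol itself treats a patient's charges as showing which injection was given. The hold is patient by patient: "billing / charges will be held until the patient reaches the final endpoint of the study or withdraws from the study". The task then goes to the coordinator: "The research coordinator will be the study personnel who records the billing at this point, however, all outcome assessments will have been completed already".

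Three other statements bear on this:

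- **Randomization.** The same section says "Enrolled patients will be assigned to one of two treatment arms using a block randomization scheme". It gives no block size, does not say whether sizes vary, and does not say whether they are kept from the coordinator.
- **Accrual.** Selection of Subjects says "We aim to recruit 116 patients over 1 year".
- **Follow-up.** Patient Outcome Measures schedules assessments at 2 weeks, 2 months and 4 months by mail, electronic means or telephone. The primary endpoint is at 2 months; all 4-month measures are secondary.

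Subject Recruitment and Compensation has the coordinator take written consent on the day of the procedure, so the coordinator can see the order of enrolment.

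**The concern.** The safeguard answers one question: can the coordinator's knowledge of a patient's arm affect that patient's own assessments? It cannot, because those are finished. It leaves open what that knowledge says about patients still being followed. In a balanced block the assignments are dependent, and once enough of them are known the rest follow. An assessor who learns arms one at a time, while block-mates are waiting for their 4-month contact, may be able to work out or guess some of the remaining arms.

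At stake is the credibility of the 4-month NRS, NDI, EQ-5D and WAI, chiefly where they are taken by telephone. The treating physicians cannot be blinded, so the follow-up data lean on patient and assessor blinding. The Bang index is planned for patients only, so a leak to the assessor would not be detected.

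**Working it through.** **Inputs from the plan.** N = 116, accrual 12 months, last assessment at 4 months, primary endpoint at 2 months, block randomization in two arms. The plan gives no figure for assessor blinding, so there is none to reproduce. The N used here does reproduce: with 45% and 70% response, two-sided alpha 0.05, power 0.80 and unpooled variance, n per arm = (0.45×0.55 + 0.70×0.30) × (1.960 + 0.842)² / 0.25² = 57.45, the stated 57.5. Nothing below disputes it.

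**Assumptions, not in the plan.** Uniform accrual; fixed 1:1 blocks whose size and order the coordinator knows; a stated delay from the 4-month assessment to billing entry; no withdrawals unless noted.

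**Step 1: is anyone still being followed when arms are released?** Accrual is 116/12 = 9.7 patients a month, so about 9.7 × 4 = 39 are in follow-up at a time during steady accrual. With same-day billing, every 4-month assessment except the first (115/116 = 99%) comes after at least one other patient's arm has been released.

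**Step 2: arms fully determined, same-day billing.** In a balanced block of 2k, the expected number of assignments fixed by the earlier ones is 2k/(k+1), a share of 1/(k+1). Counting complete blocks in 116 patients (an incomplete last block adds none here):

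| Block size | Share | Complete blocks × determined per block | Determined of 116 |
|---|---|---|---|
| 4 | 33% | 29 × 1.333 | 38.7 |
| 6 | 25% | 19 × 1.5 | 28.5 |
| 8 | 20% | 14 × 1.6 | 22.4 |

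Simulation agrees. Outside this range, blocks of 2 give 50% and blocks of 20 about 8%. The best-guess accuracy for blocks of 4, 6 and 8 is 71%, 68% and 66%, against 50% by chance.

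**Step 3: allow a billing delay.** Patients arrive about 365/116 = 3.15 days apart, so a block of 4 spans about 9 days and a short delay matters. With a delay of d days and x = d/3.15, treating gaps between arrivals as exponential, the third patient in a block of 4 is determined with probability e^(−x)/3. The fourth is determined with probability e^(−x) + x·e^(−x)/3. The sum per block is e^(−x)(4 + x)/3, over 29 blocks:

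- d = 0: 29 × 1.333 = 38.7
- d = 3 (x = 0.953): 29 × 0.636 = 18.5
- d = 7 (x = 2.22): 29 × 0.224 = 6.5
- d = 14 (x = 4.45): 29 × 0.033 = 1.0

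Simulated counts at 3, 7, 14 and 30 days are about 15, 6, 1 and 0 for blocks of 6, and about 12, 5, 1 and 0 for blocks of 8. Best-guess accuracy also falls toward 50% as billing lags.

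**Step 4: withdrawals.** If 10% to 20% withdraw at times spread evenly over the 4 months, the determined share at 4 months with same-day billing and blocks of 4 rises from 33% to 37–41%.

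**Step 5: the 2-month primary endpoint.** A completer's billing can inform a 2-month assessment only if the two patients enrolled more than 2 months apart, and about 9.7 × 2 = 19 patients enrol in that time. A block would have to span roughly 20 or more patients. For small blocks the determined share is 0% without withdrawals. With 10–20% withdrawals it is 0.2–0.9% for blocks of 4 and 5–10% for blocks of 2.

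**The case against.** A reader might infer that the assessor is unblinded for later 4-month assessments, or that the claimed blinding fails outright. The documents do not support that. No patient's own billing reaches the coordinator before that patient's assessments end. Another patient's arm can only be inferred, and certain inference needs small fixed blocks, knowledge of their size and order, and billing within days. The plan states none of these. Even with blocks of 4 and same-day billing, about two thirds of 4-month arms would not be certain.

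Nor should the 39 be read as an expected count. It is the zero-delay case, and at one to two weeks it falls to between about 7 and 1. The outcomes are patient-reported, patients are to be blinded until their own participation ends, and contact may be by mail or electronically, so the assessor's room to influence answers is mainly on the telephone. The telephone share is not given. The primary endpoint is at 2 months.

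All of this stands and limits the size of the problem. It does not restore the safeguard, whose reasoning covers only the patient being billed. It might also be said that the billing recorder is a different coordinator from the assessor. The plan's own argument, that the recorder stays unbiased because assessments are already complete, makes sense only if they are the same role.

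**Conclusion.** The point holds as a gap in assurance. The plan promises an assessor blinded throughout, yet gives that role a task which releases assignments while other patients are being followed. Assessor blinding is therefore not assured for the secondary 4-month endpoints. For assumed known, fixed blocks of 4 to 8 and no withdrawals, the fully determined 4-month assessments number about 39 to 22 of 116 with same-day billing, about 7 to 5 at 7 days, and about 1 at 14 days. The true figure cannot be fixed from the documents and could be close to zero if block sizes vary and are concealed. A claim that the primary result is compromised would not be supported, and no error in sample size or power follows. This is a minor point, worth correcting because the correction is nearly free.

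**What to change.** In Design & Procedures, delete the sentence that has the research coordinator record billing. State instead that procedure-team staff who already know the assignment will record it, still held until that patient finishes or withdraws. Add that block sizes are kept from the coordinator. Patients are also unblinded at the end of their participation, and the plan does not say who tells them; this too should not pass through the assessor.

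The cost is a small reassignment of an existing task, with no extra staff and no change in N. With the assignment no longer passing to the assessor, deduction through billing falls to 0% and guessing returns to 50%. Holding all billing until the last patient's 4-month assessment would also work, but that falls at about month 12 + 4 = 16, against month 4 for the first patient. It would delay early charges by up to about a year and is not needed.

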Comparison of cervical transforaminal epidural corticosteroid injections with lateralized interlaminar epidural corticosteroid injections for treatment of cervicogenic upper extremity radiculopathy

NCT03389620

Document Date: 11/15/2022

Purpose of the Study

Our central hypothesis is that the innovative CT fluoroscopy-guided lateralized interlaminar epidural corticosteroid injection technique will exhibit superior or equivalent efficacy to the traditional transforaminal method for treatment of cervicogenic upper extremity radiculopathy.

SPECIFIC AIM 1: Compare the efficacy of CT fluoroscopy-guided LILESI to that of CT fluoroscopy-guided TFESI in the treatment of patients with cervicogenic upper extremity radiculopathy.

HYPOTHESIS 1: Patient outcomes will be equivalent between the two injection techniques.

1.1 Compare the difference in the primary outcome measure between the two patient groups: numerical pain rating scale (averaged over the past 24 hours) at two months.

1.2 Compare the difference in secondary outcome measures between the two patient groups: numerical pain rating scale (averaged over the past 24 hours) at 2 weeks and 4 months; neck disability index, EQ-5D, and work ability index at 2 weeks, 2 months, and 4 months.

SPECIFIC AIM 2: Compare complication rates between the two injection techniques.

HYPOTHESIS 2: No difference will be seen in complication rates between the two injection techniques.

2.1 Determine the frequency of minor and major adverse events for each group immediately post-procedure and at 2 days after the procedure.

SPECIFIC AIM 3: Determine the technical success rate, defined as the spread of the contrast epidurogram into the neuroforamen, for each of the two injection techniques.

HYPOTHESIS 3.1: The contrast epidurogram will extend into the neuroforamen more frequently with the lateralized interlaminar approach than with the transforaminal approach.

3.1 Determine the frequency of contrast spread into the neuroforamen for each group.

HYPOTHESIS 3.2: Inadvertent intravascular injection will occur more frequently with the transforaminal approach.

3.2 Determine the frequency of inadvertent intravascular contrast injections for each group.

Background & Significance

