Patients randomized to undergo LILESI will be placed prone on the CT gantry table. A planning CT will be obtained through the area of interest. Acquired images will allow for planning a posterior approach lateralized interlaminar needle trajectory to the dorsal epidural space. The skin surface will then be marked, sterilized, draped, and anesthetized. A 22-gauge 3.5 inch Quincke tip spinal needle will be advanced under intermittent CT fluoroscopic guidance into the lateral dorsal epidural space (Figure 2). On reaching the target, heme-negative aspiration will be confirmed. Next, approximately 0.2 mL of contrast material (iopamidol; Isovue-M 200, Bracco Diagnostics, Princeton, NJ) diluted 1:3 with preservative free normal saline will be injected to assess needle tip position and potential future medication spread. Intravascular injection will be excluded using a “double-tap” technique. After visual confirmation of correct needle tip position, 0.8 mL of dexamethasone (10 mg/mL) will slowly be injected over a period of approximately 30 seconds. On completion of the procedure, the patient will be observed for 30 minutes in the Radiology Observation unit.

Patient Outcome Measures

Prior to the procedure, baseline outcome measures of NRS, NDI, EQ-5D and WAI will be determined (see Outcome Measures below for description). Immediately post-procedure, NRS will be reacquired. NRS, NDI, EQ-5D and WAI will then also be acquired via mail, electronic communication, or telephone call at 2 weeks, 2 months, and 4 months post-procedure. The primary endpoint will be NRS (averaged over the past 24 hours) obtained at 2 months after the procedure. Secondary endpoints will include NRS at 2 weeks and 4 months after the procedure as well as NDI, EQ-5D and WAI at 2 weeks, 2 months, and 4 months after the procedure.

Adverse Events

Patients will be screened for adverse events immediately after the procedure as well as via phone call at 2 days post-procedure. While all adverse events will be recorded, the following will be considered major adverse events: stroke, paralysis, or other permanent neurologic deficit; allergic reaction; hospitalization or ER visit. Minor adverse events will include, but not be limited to: nausea / vomiting, dizziness, headache, symptomatic hypertension, vasovagal reaction, fever / chills, facial flushing, insomnia, and pain exacerbation.

Epidurogram

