Study participants will be randomized to receive a cervical epidural steroid injection of 0.8 mL of dexamethasone (10 mg/mL) through either a lateralized interlaminar or a transforaminal route. Cervical epidural injections via both routes have had reports of minor (increased pain, passing out, headaches, insomnia, hiccups, minor allergic reactions) and major (bleeding, major allergic reaction, paralysis,

stroke, death) adverse events. These would be disclosed to the patient during the process of informed consent for the procedure. Even though patients may provide consent to a cervical epidural steroid injection, we acknowledge that this protocol involves removing participant and provider choice and randomizing participants to one route or another. However, the peer-reviewed literature is clear that there is no data to support the notion that one route exposes a recipient to increased risk (23) and both routes continue to endorsed in the most recent edition of Spine Intervention Society Guidelines.(24) This protocol will mitigate procedural risks through the exclusion of any prospective participants where such injections are contraindicated; and through the use of highly-experienced and fellowship trained operators, using image-guidance, contrast-confirmation, and non-particulate dexamethasone consistent with the Multi-Disciplinary Pain Working Group's recommendations (25) and Spine Intervention Society Guidelines.(24) Any adverse events will be reported according to protocol.

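### Adverse events are actively elicited only just after the procedure and at day 2, although the major-event definition has no time limit and three later contacts are already scheduled

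*Combined protocol and SAP*

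**What the plan says.** All references are to the combined protocol and SAP.

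- **Timing of screening.** Adverse Events: "Patients will be screened for adverse events immediately after the procedure as well as via phone call at 2 days post-procedure". Specific Aim 2.1 matches it: "Determine the frequency of minor and major adverse events for each group immediately post-procedure and at 2 days after the procedure". The two sections agree.
- **Major events.** Adverse Events lists "stroke, paralysis, or other permanent neurologic deficit; allergic reaction; hospitalization or ER visit". It attaches no time window to any of these and does not require the event to be related to the injection.
- **Later contacts.** Patient Outcome Measures: "NRS, NDI, EQ-5D and WAI will then also be acquired via mail, electronic communication, or telephone call at 2 weeks, 2 months, and 4 months". No adverse-event item is listed for them.
- **General statements.** Adverse Events also says "While all adverse events will be recorded", and Risk/Benefit Assessment says "Any adverse events will be reported according to protocol". Neither names a question, time point or route of collection after day 2.
- **Where the data are used.** Aim 2 compares complication rates between the techniques, and Hypothesis 2 expects no difference. The interim analysis of the first 58 patients is also to evaluate safety.
- **Crossover.** Persistently symptomatic patients in either arm may cross over at 2 months. No adverse-event screen is stated specifically for that second injection.

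**The concern.** The schedule for asking about adverse events does not fit the plan's own definition of a major one. A deficit present at day 2 can be called permanent or transient only after more time has passed, and no later check is stated. A hospitalization or ER visit on day 3 or afterwards meets the definition as written, but nobody is scheduled to ask about it.

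What is at stake is the meaning of the Aim 2 safety statement. If the trial reports no major events, a reader who has seen a definition without a time limit and a 4-month follow-up may take that to cover the whole follow-up, when it covers two days. The gap is avoidable, because every patient is due to be contacted three more times.

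**Working it through.** **1. The passages side by side**

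| Major-event component | Can day 0 and day 2 screening settle it? | Later planned question? |
|---|---|---|
| Permanent neurologic deficit | Onset by day 2, yes; permanence, no | None stated |
| Hospitalization or ER visit by day 2 | Yes | Not needed |
| Hospitalization or ER visit after day 2 | No | None stated |
| Stroke or paralysis first evident after day 2 | No | None stated |

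This step needs no event rate. There are 2 points of active elicitation and 3 later contacts without an adverse-event item. Taking 4 months as about 120 days, the window covers 2/120 = 1.7% of follow-up time. That is a share of time and says nothing about the share of risk.

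**2. The denominator**

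The plan gives no figure for adverse-event rates or safety power. Its only relevant number is the sample size, which reproduces. With response rates of 45% and 70%, power 0.80 and two-sided alpha 0.05 (sidedness is not stated; two-sided is the reading that fits), the unpooled formula gives

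n per arm = (1.960 + 0.842)² × (0.45×0.55 + 0.70×0.30) / 0.25² = 57.45,

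in line with the stated 57.5 per arm and 116 in total. I use 116 overall and 58 per arm.

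**3. What zero observed major events would show**

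The one-sided 95% upper bound is 1 − 0.05^(1/n).

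- n = 58: 5.0% per arm.
- n = 116: 2.5% overall.

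Under the present schedule both bounds apply to 2-day risk only.

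**4. Size under an assumed late-event rate**

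The documents give neither a rate nor a timing for major events. Let p be the assumed proportion of patients with a qualifying event first evident after day 2, and c the assumed proportion of such events that reach the record by spontaneous report.

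- Expected late events = 116 × p.
- Chance that at least one occurs = 1 − (1 − p)^116.
- Chance that at least one is missed = 1 − (1 − p(1 − c))^116.

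| Assumed p | Expected late events | At least one occurs | At least one missed if c = 50% |
|---|---|---|---|
| 0.5% | 0.6 | 0.44 | 0.25 |
| 1% | 1.2 | 0.69 | 0.44 |
| 3% | 3.5 | 0.97 | 0.83 |

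The third column equals the chance of missing an event only if c = 0.

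**5. Effect on the between-arm comparison**

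At 58 per arm, Fisher's exact test gives p = 1.0 for 1 versus 0 events. For 2 versus 0, p = 2 × C(58,2)/C(116,2) = 2 × 1653/6670 = 0.50. One or two additional events would not change the test result.

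**The case against.** The strongest reply is that the window is a declared choice. Aim 2.1 defines its measure as frequency at the two early time points, and the Adverse Events section follows it. For that measure, later events fall outside the scope and are not undercounted. A short window is also a defensible way to describe complications of a single injection. This stands: there is no contradiction about timing, and the plan does not misstate its own measure. What remains is the mismatch with a major-event definition that has no time limit and includes permanence.

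A second reply is that the plan promises to record all adverse events. This stands in part. A reader might infer that late events will go unrecorded, and the documents do not support that, because a patient may volunteer one, including at a later contact. The gap is in systematic asking, and volunteered reports are not a substitute for it.

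A third reply is that a longer window brings in noise. Any hospitalization or ER visit counts as major whatever its cause, so four months of follow-up would collect unrelated events, and crossover injections would blur attribution. This also stands, and it is why the later data need a relatedness judgement and should not replace the early comparison.

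One could instead simply limit the definition to two days. That would make the text consistent, but permanence would still be unclassifiable.

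**Conclusion.** The gap holds on the text alone. Followed exactly, the schedule cannot establish permanence of a deficit and has no systematic route for major events first evident after day 2. Such events can be missed, and a statement that none occurred would describe 2-day risk only.

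The size is not known from the documents. At an assumed 0.5% to 3% of 116 patients, 0.6 to 3.5 late events are expected, with a 0.44 to 0.97 chance that at least one occurs and is at risk of being missed. The chance that one is actually missed is lower if some are volunteered: 0.44 in place of 0.69 at a 1% rate with half reported spontaneously.

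Two stronger readings are tempting and are not supported. The first is that the planned complication rates are understated: for the declared day 0 to 2 measure they are not. The second is that one or two extra events would overturn the Aim 2 comparison: the exact tests above show they would not. What they could change is a descriptive statement of no major events. The efficacy analysis and sample size are unaffected.

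**What to change.** - **Keep** the day 0 to 2 frequencies as the planned Aim 2 comparison.
- **Add** the same adverse-event items to the 2-week, 2-month and 4-month forms or calls, asking explicitly about hospitalization, ER visits and persisting neurologic deficit. Amend Aim 2.1, Patient Outcome Measures and Adverse Events to match.
- **Classify** each deficit as permanent or resolved at the patient's last contact, and say so in the definition.
- **Report** cumulative events to 4 months by randomized arm, descriptively. Include a relatedness judgement made blind to arm where possible, and flag events after a crossover injection. State how many patients answered at each contact.

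The cost is a short amendment and a few questions at contacts already planned. The number of active elicitation points rises from 2 to 5. The outcome assessor is already blinded, so collection can be blind too. The drawbacks are some unrelated events that the relatedness judgement must separate, and incomplete capture where mailed or electronic contacts go unanswered.

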The primary investigator will retrospectively evaluate epidurographic contrast material spread through review of the procedural images at the completion of the study. The leading edge of resultant contrast during both the TFESI and LIESI groups will be categorized as either within the spinal canal, intraforaminal, or extraforaminal, as previously described in publications by our group (see Figure 1B) (11). The presence of inadvertent intravascular injection will also be noted, as previously described by our group (10).

Crossover, Withdrawal, or Missing Data

We will employ an intention-to-treat (ITT) analysis for this trial [49]. All persistently symptomatic patients, regardless of study arm (i.e. both LIESI and TFESI), will be allowed to crossover at the 2-month time point. Patients that crossover between study arms, withdraw from the study, or for whom there is missing data will all be handled in the same manner: we will conservatively assume that no further benefit will be gained from the initial treatment. As such, the most recent available outcomes data will be extrapolated to all later time points for which no data are available. Patients will be allowed to withdraw from the study and terminate their participation at any time.

Interim Data Analysis

An interim analysis will be performed of the first 58 patients by the biostatistician. All study participants, outcome assessors, and other personnel will remain blinded. Safety and efficacy will be evaluated using an O'Brien–Fleming stopping rule of $p < 0.001$ in order to evaluate for early evidence of treatment efficacy [48].

Outcome Measures

Numerical Rating Scale (NRS)

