Based on a power of 0.8 (alpha 0.05) to detect superiority of the LILESI group, assuming positive response rates of 45% for the TFESI group and 70% for the LILESI group, we would need a total of 116 patients (57.5 patients in each arm). This sample size would also give us a power of 0.99 to detect non-inferiority (i.e. equivalence between TFESI and LILESI) (non-inferiority margin 0.1).

Patient Outcome Analysis

A reduction of 2 points from baseline on the NRS will be considered a positive response (clinically meaningful or moderate improvement per IMMPACT consensus statement) (15). Primary Endpoint (average NRS over the past 24 hours at 2 months time point): We will apply a difference test and a non-superiority test for binomial proportion to test the primary endpoint. Secondary Endpoints: The secondary endpoints will be analyzed using a test for difference in binomial proportions or a t-test for binomial or semi-continuous variables, respectively.

Interim Data Analysis

An interim analysis will be performed of the first 58 patients by the biostatistician (co-investigator). All study participants, assessors, and other personnel (including other co-investigators) will remain blinded. Safety and efficacy will be evaluated using an O'Brien–Fleming stopping rule of $p < 0.001$ for the interim analysis in order to evaluate for early evidence of treatment efficacy (26).

Crossover, Withdrawal, or Missing Data

We will employ an intention-to-treat (ITT) analysis for this trial (27). Patients that crossover between study arms, withdraw from the study, or for whom there is missing data will all be handled in the same manner. A conservative approach will be taken and we will assume that the patient will receive no further benefit from the study injection. As such, the most recent available outcomes data will be extrapolated to all later time points for which no data are available.

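### Carrying the last score forward into the 2-month primary endpoint is not assured to be conservative for non-inferiority, and no sensitivity analysis is planned

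*Combined protocol and SAP*

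**What the plan says.** Both sections headed Crossover, Withdrawal, or Missing Data (one under Design & Procedures, one under Data Analysis & Statistical Considerations) give a single rule for crossover, withdrawal and missing data: "the most recent available outcomes data will be extrapolated to all later time points for which no data are available". The design section justifies it thus: "we will conservatively assume that no further benefit will be gained from the initial treatment". The statistics section says: "A conservative approach will be taken and we will assume that the patient will receive no further benefit from the study injection".

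The primary endpoint is the NRS at 2 months, and Patient Outcome Analysis turns it into a responder endpoint: "A reduction of 2 points from baseline on the NRS will be considered a positive response". The same section says: "We will apply a difference test and a non-superiority test for binomial proportion to test the primary endpoint". Sample Size Determination claims a "power of 0.99 to detect non-inferiority" with a "non-inferiority margin 0.1". I read the test called non-superiority as this non-inferiority test. Hypothesis 1 is that outcomes are equivalent.

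Patient Outcome Measures takes an NRS immediately after the procedure, then at 2 weeks, 2 months and 4 months. Nothing excludes the procedure-day score from being carried forward. No sensitivity analysis, alternative method or expected rate of missing data appears.

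**The concern.** Assuming no further benefit sounds cautious, but carry-forward also assumes no loss of benefit. A patient who responded at 2 weeks, whose relief then faded and whose 2-month score is missing, still counts as a 2-month responder.

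Whether this helps or harms a test depends on how it acts on the difference between arms. A fill that pulls the arms together works against a superiority claim but in favour of a non-inferiority claim, and non-inferiority is the conclusion closest to Hypothesis 1. With no second analysis, a reader could not tell whether a non-inferiority result rests on observed or filled scores, or in which direction the filled scores moved it.

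The procedure-day NRS adds a separate problem. If the 2-week and 2-month scores are both missing, the rule as written uses a score taken minutes after the injection as the 2-month outcome.

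**Working it through.** **The plan's own figures.** With unpooled variance and two-sided 0.05, the size per arm is (1.960 + 0.842)² × (0.45×0.55 + 0.70×0.30) / 0.25² = 57.45. That gives 58 per arm and 116 in total, as stated, with nothing added for missing data. For non-inferiority at 45% vs 70%, SE = √[(0.2475 + 0.2100)/58] = 0.0888. Power is Φ(0.35/0.0888 − 1.645) = 0.989 at one-sided 0.05, or 0.976 at one-sided 0.025. The sidedness is not stated; the claimed 0.99 fits one-sided 0.05 better. I give both.

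**Bias.** Let m_T and m_L be the shares filled in each arm. The bias in LILESI minus TFESI is

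m_L × (carried − true response in filled LILESI patients) − m_T × (carried − true response in filled TFESI patients).

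The sign is open. If m_L = m_T = m and carried response is the same in both arms, a true difference shrinks to (1 − m) of its value, provided filled patients have the same true difference as the rest.

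**Size at the margin.** Assumptions: 58 per arm; true response 45% TFESI and 35% LILESI, also among filled patients; carried response f_T and f_L. Then p_T = 0.45(1 − m_T) + m_T f_T, p_L = 0.35(1 − m_L) + m_L f_L, and false non-inferiority = Φ[(p_L − p_T + 0.10)/SE − z].

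Example with m = 0.20 and f = 0.60 in both arms: p_T = 0.48, p_L = 0.40, SE = 0.0919, and Φ(0.02/0.0919 − 1.960) = 0.041.

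False non-inferiority at 5/10/20% filled in both arms:

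| Carried response, TFESI / LILESI | One-sided 0.025 | One-sided 0.05 |
|---|---|---|
| 60% / 60% | 2.8 / 3.2 / 4.1% | 5.6 / 6.2 / 7.7% |
| 60% / 50% | 2.5% throughout | 5.0% throughout |
| 60% / 45% | 2.3 / 2.2 / 1.9% | 4.7 / 4.5 / 4.0% |
| 50% / 70% (constructed adverse case) | 3.6 / 5.1 / 9.5% | 6.9 / 9.4 / 16.0% |

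**Unequal shares.** The second row is unbiased only because the shares are equal. With 5% of TFESI and 15% of LILESI filled, the bias is 0.15×0.15 − 0.05×0.15 = +0.015. Then p_T = 0.4575, p_L = 0.3725, SE = 0.0912, and false non-inferiority is 3.6% at one-sided 0.025. With the shares reversed it is 1.7%.

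**Simulation check.** Design: 20% missing at random, 2-week score always observed, 2-month response 4 times as likely in 2-week responders, 20 imputations by arm from 2-week response, one-sided 0.025. Carry-forward gives 4.3%, 2.7%, 2.1% and 10.0% in the four rows. Multiple imputation gives 2.6–2.7% in all four.

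**Superiority power at 45% vs 70%, 20% filled.** With 60% carried in both arms: p_T = 0.48, p_L = 0.68, SE = 0.0898, power Φ(0.20/0.0898 − 1.960) = 0.61. If the 25-point gap is already present at 2 weeks (50% vs 75%): p_T = 0.46, p_L = 0.71, SE = 0.0885, power 0.81; simulation gives 0.79–0.81.

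**Procedure-day NRS.** The NRS section applies a 24-hour average at all time points but also describes the scale as rating current pain. A 24-hour average taken just after the injection would mostly reflect pain before it, and would tend to make the patient a non-responder. A current-pain score could be affected by the lidocaine test injection, which is described for TFESI and not for LILESI. The documents do not allow this effect to be sized, and the simulation does not include it.

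**The case against.** Several points on the other side are fair.

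- *Missingness may be low.* Selection of Subjects excludes patients not expected to complete follow-up, and scores can be collected by mail, electronically or by telephone. At 5–10% filled with the same carried response in both arms, the error moves only from 2.5% to 2.8–3.2%. This stands and limits the weight of the point.
- *The adverse case is constructed.* It needs a 20-point LILESI lead at 2 weeks to become a 10-point deficit at 2 months. Nothing in the documents suggests that, so 9.5% shows how far the error can go and is not a forecast.
- *The plan never claims conservatism for the non-inferiority test.* It applies the word to the assumption about the patient's benefit, and the sample size is set on superiority. That is correct. The point is only that the label cannot be relied on for the non-inferiority conclusion.
- *Imputation does well in the simulation by design.* It uses the variables that generate the data and the missingness. This too stands: the simulation says nothing about missingness that depends on unseen pain.

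A reader might go further than the documents allow in three ways. One is to infer that carry-forward always favours non-inferiority; the 60%/50% and 60%/45% rows show no bias and protection. Another is to infer that it always costs superiority power. The 0.61 figure needs LILESI response to rise from 60% to 70% while TFESI falls from 60% to 45%; with the gap present early, power is kept. The third is that crossover contaminates the primary endpoint. Persistently symptomatic patients "will be allowed to crossover at the 2-month time point", so that part of the rule mainly affects the 4-month outcomes.

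**Conclusion.** The point holds in a limited form. The protocol fills missing 2-month primary scores by carry-forward, calls the assumption conservative and offers no check on it. The resulting error in the 0.1-margin test can go either way. Across the assumed patterns with equal shares of 5–20% filled, false non-inferiority runs from 1.9% to 9.5% against 2.5%, and the top of that range comes only from the adverse case. With 5% and 15% filled in the two arms, the 60%/50% pattern gives 3.6% or 1.7%, depending on which arm loses more.

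All these sizes rest on assumed missing rates and carried response rates, because the documents give neither. The effect is small at low missingness unless the arms differ in early response or in dropout. The gap over the procedure-day NRS is real on the text, but its effect is unquantified and of unknown direction. This is a change that should be made, at the lower end of that grade.

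**What to change.** (a) State that the procedure-day NRS never fills a later time point.

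(b) Analyse the 2-month responder endpoint with multiple imputation by arm from baseline and 2-week NRS. Make this the primary analysis or, at the least, a pre-specified sensitivity analysis beside carry-forward from 2 weeks at the earliest.

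(c) Add a tipping-point analysis for non-inferiority that varies the response of missing patients separately by arm, up to LILESI missing = non-responder with TFESI missing = responder. Counting all missing patients as non-responders is not enough by itself: with equal missingness it also pulls the arms together.

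(d) Do not rely on carry-forward as conservative for the non-inferiority conclusion.

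**Cost.** SAP wording, modest analysis work and no new data. In simulation, imputation gives a standard error about 8% larger than carry-forward at 20% missing. Superiority power is about 0.76–0.77 at 10% missing and 0.72–0.73 at 20%, against the planned 0.80. Most of that loss comes from having fewer observed scores: the observed-only formula gives 0.76 and 0.71. Imputation assumes that missingness depends only on observed data, and for patients with no 2-week score it has only arm and baseline NRS to use. It therefore does not replace the tipping-point analysis.
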